### D.2.b. Additional biomarkers

As noted earlier, a panel of investigators across multiple sites with experience in the development of biomarkers for severe affective disorders and with the treatment of depression using IV ketamine will identify additional specific blood-based biomarkers for predicting antidepressant response to ketamine in adults with treatment-resistant unipolar or bipolar major depression. The development of these additional biomarkers will be facilitated using the same clinical data and biological samples obtained as part of the proposed core clinical protocol. Therefore, multiple biomarkers will be developed from a single protocol. These are discussed further below.

## E. STUDY CONDUCT

### E.1. Study Overview

As noted above, the two main components of this study are the core clinical protocol (administration of ketamine, collection of clinical outcomes data) and biomarker sampling and analysis. In broad terms, the core clinical protocol will consist of a multi-site, single-arm, open label clinical trial of 100 adult patients (enrolled at 4 clinical sites) with treatment-resistant MDD or BP given IV infusions of ketamine at subanesthetic doses (0.5 mg/kg, infused over 40 minutes or 100 minutes) (**Fig. 2**). The core clinical protocol will consist of a mandatory acute phase (all clinical sites) and an optional continuation phase (each site may choose to participate or not). During the mandatory **acute phase**, a total of 3 ketamine infusions will be given at least every other day (minimum 1 day between infusions, and a maximum of 4 days between infusions), during a time window of up to 11 days. Biological samples for biomarker development will be obtained before and after each acute phase infusion. Patients who achieve remission of depressive symptoms and suicidal ideation during the acute phase will be eligible for the optional **continuation phase**. For sites that choose to offer continuation phase treatment, patients who respond to or remit (defined below) during the acute phase will receive 4 additional, once weekly continuation phase IV ketamine infusions. Biological specimens will not be collected during the optional continuation phase. At Mayo Clinic-Rochester, these specimens will be collected by the Center for Clinical and Translational Science Clinical Research Unit (CRU), either by mobile staff (inpatients) or at the CRU site (outpatients) where staff will collaborate to prepare infusion logistics, establish venipuncture site, monitor infusion and vital signs during and after infusion (60 minutes).

**Figure 2 Study Overview.** The core clinical protocol consists of a mandatory acute phase and an optional continuation phase (Panel A). Up to 11 days are allowed including the first infusion day (Day 1) to administer 3 IV ketamine infusions (0.5 mg/kg, 100 minutes) during the acute phase. Acute phase remitters at specific sites may receive continuation phase infusions. Biological sample collection schedule is summarized in Panel B.

Depressive symptoms, response, remission, suicidality, and global clinical state will be assessed at baseline prior to each ketamine infusion, at the end of infusion (40 or 100 minutes), at the end of post-ketamine infusion observation (60 minutes), and 24 hours after each infusion during the acute and continuation phases, using standardized rating scales. Safety measures will include standardized questionnaires and an open-ended side effect questionnaire. Concerns that arise about worsening suicidality or other psychiatric emergencies will prompt further evaluation by a board certified study psychiatrist, who will determine the need for additional assessment and follow-up.

## E.2 Protocol, Protocol Amendments and Pre-Initiation Documentation

Neither the sponsor nor the investigators will modify this protocol without a formal amendment by the sponsor. All protocol amendments must be issued by the sponsor, and signed and dated by the investigator and approved by site IRB/IEC. Protocol amendments must not be implemented without prior IRB/IEC approval, except when necessary to eliminate immediate hazards to the subjects, in which case the amendment must be promptly submitted to the IRB/IEC and relevant competent authority.

Documentation of amendment approval by the investigator and IRB/IEC must be provided to the sponsor. During the course of the study, a situation may arise where a departure from the protocol is necessary and unavoidable. In such an instance, the investigator or appropriate study-site personnel will contact the sponsor. Except in emergency situations, this contact should be made before implementing any departure from the protocol. In all cases, contact with the sponsor must be made as soon as possible to discuss the situation and agree on an appropriate course of action. The data recorded in the CRF and source documents will reflect any departure from the protocol, and the source documents will describe this departure and the circumstances requiring it.

Pre-initiation documentation must be provided to the sponsor before the protocol is implemented at each site. Each site will be provided with a separate document identifying all pre-initiation documents required to be provided to the sponsor, and another pre-enrollment list of documents required by the sponsor before enrollment of first subject.

## E.3. Inclusion Criteria

For inclusion in this study, the following are required:

- Ability to provide informed consent;
- Current psychiatric inpatient (voluntary only) or outpatient treatment;
- Male or female;
- Age 18-65 years;
- Meets DSM-5 diagnostic criteria for major depressive disorder, bipolar I disorder, or bipolar II disorder;
- PHQ-9 total score  $\geq 15$  at screening and at baseline (just prior to first acute phase ketamine infusion);
- Treatment-resistant depression, as defined by failure of at least two previous antidepressant or mood stabilizing treatments within the current depressive episode. Failed antidepressant or mood stabilizing treatments can include pharmacotherapy for depression at an adequate dose for at least 8 weeks, or an acute series of at least 6 administrations of electroconvulsive therapy (ECT);
- Ability to pass a comprehension assessment test related to effects of ketamine and trial objectives and criteria.

## E.4. Exclusion Criteria

Based on ketamine's known difficulties with induction of perceptual/psychomimetic symptoms, exclusion criteria for this study are as follows:

- Patients with a BMI  $>40$ .
- Diagnosis of schizophrenia, schizoaffective disorder, or active psychotic symptoms;
- Ongoing prescription of  $\geq 4$  mg lorazepam equivalents (total) daily, or morning dosing of any benzodiazepine at the time of assessment;
- Currently undergoing ECT, transcranial magnetic stimulation, vagal nerve stimulation, or deep brain stimulation as either an acute or maintenance treatment of depression;
- Any active or unstable medical condition judged by the study psychiatrist as conferring too great a level of medical risk to allow inclusion in the study;

- A cannabis use disorder by DSM-5 criteria in partial remission of less than 3 months will be an exclusion from enrollment. Cannabis use disorders in partial remission of at least 3 months will defer this exclusion.
- Any patient-reported abuse or dependence of cannabis within the prior 3 months from date of screening will be an exclusion.
- Any positive urine toxicology screen as part of the screening visit for illicit, non-prescribed, drug use will be an exclusion.;
- Any current abuse or dependence of alcohol or drugs (excluding nicotine, caffeine, and cannabis). Note: Persons will be allowed to enroll in this study if their drug or alcohol abuse/dependence is in complete (not partial) and sustained (> 1 year) remission;
- Use of any MAOI is prohibited two weeks prior to administration of study drug; if patients are on an MAOI when enrolled, study drug will not be administered until two weeks off MAOI.
- CYP3A4 inducers carbamazepine and modafinil are prohibited two weeks prior to administration of study drug and at least 24 hours after last dose of study drug.
- Current use of Naltrexone.
- History of traumatic brain injury that resulted in loss of consciousness;
- Developmental delay, mental retardation, or intellectual disorder;
- Clinical or self-reported diagnosis of delirium, encephalopathy, or related clinical diagnosis within the prior 12 months;
- Cognitive disorder (mild and major categories per DSM-5);
- Current or prior clinical treatment by ketamine for depression or prior or current participation in another study of ketamine for depression within the prior 6 months.;
- History of either poor antidepressive response to or poor tolerability of ketamine (any route of administration) when previously administered for treating symptoms of depression;
- History of hypothyroidism unless taking a stable dose of thyroid medication and asymptomatic for 6 months;
- Significant unstable medical condition
- Hepatic insufficiency (2.5 X ULN for AST or ALT) within 1 year of consent, past liver transplant recipient, and/or clinical diagnosis of cirrhosis of the liver;
- A diagnosis of Complex Regional Pain Syndrome (CRPS);
- Males active in attempting to conceive a child.
- Pregnancy, or nursing;
- Prisoners;
- Involuntary psychiatric hospitalization.

## E.5. Subject Recruitment and Screening

### E.5.a. Overview

Subjects will be patients recruited from either outpatient clinics or adult inpatient psychiatric units, and provide voluntary informed consent to participate in the study. Each study site will retain decisional authority as to whether recruitment at their site will occur in outpatient setting, inpatient settings, or both. Patients will be identified for potential inclusion in the study by study coordinators or other study personnel designated by the site lead investigator. Eligible patients will be approached by study staff and the elements of the study will be explained. If the patient meets all inclusion and no exclusion criteria, a site investigator (not providing care for the patient), will further describe the protocol to patient, administer the comprehension assessment test (detailed below), and obtain informed consent. Patients will have the opportunity to have an IRB patient advocate or a significant other present during the consent procedure if desired. One hundred patients will be recruited in the study.

Each site will complete a screening log and subject identification log to facilitate the identification of each subject enrolled and progressed through the study. The subject identification and enrollment log will be treated as confidential, and kept in the master file at each site. All essential documents related to any subject will identify subjects by their assigned identification code and date of birth. For subjects consented and then withdrawn and not having received the first infusion of ketamine, thus no subject identification code assigned, correspondence identifying the subject will include date seen and date of birth. The screening log, made available to all sites as a separate document, reports on all subjects seen by a site investigator to determine eligibility of inclusion in the study.

#### **E.5.b. Comprehension assessment test**

A 8-question true or false quiz (comprehension assessment) based on aspects of the study will be administered to each patient, after the co-investigator explains the study, to ensure the patient understands the key concepts, potential side effects of ketamine, and goals of the study. Any incorrect answer will be reviewed by the participant and investigator with an initial by the patient with the answer that has been corrected. For any participant who answers 3 or more questions incorrectly, the study will be postponed with the patient being re-consented within the next 3 days, but no sooner than the following day. If there are still 3 or more questions answered incorrectly, the subject will not be enrolled in the study.

#### **E.5.c. Confirmation of qualifying mood disorder diagnosis**

After informed consent, major depressive disorder or bipolar I or bipolar II depression will be confirmed by the study coordinator utilizing the Depression Module of the Structured Clinical Interview for DSM-IV (SCID) [53]. The utilization of the SCID will be to define entry into the study.

#### **E.5.d. Additional screening procedures**

Assessments will also be used to confirm severity of depression and suicidal ideation, and will also serve as baseline scores at initial infusion of study drug. The PHQ-9 will be used to define a threshold score of  $\geq 15$  for enrollment into the study. All qualifying subjects will be administered the Montgomery-Åsberg Depression Scale (MÅDRS) [54] as an additional measure of depressive psychopathology, and the Suicide Status Form (SSF II-R) [55] as a measure of suicide potential. Pregnancy tests will be administered for women  $< 55$  years of age, and urine drug of abuse screens will be reviewed for all participants. The study entry criterion of having failed at least two previous antidepressant or mood stabilizing treatments within the current depressive episode will be assessed using an Antidepressant Treatment History Form (ATHF).

#### **E.5.e. Post-screening visit procedures**

Patients enrolled who continue to meet inclusion criteria will be scheduled for their first IV ketamine treatment. At this point, the research pharmacy will be contacted to prepare the ketamine infusion, and the investigator anesthesiologist will be notified of the date and time of the infusion.

### **E.6. Acute-Phase Administration of Ketamine**

All subjects at all sites will be given 3 acute-phase IV ketamine infusions (**Fig. 3**). In the acute phase, the first infusion will be provided at a 40-minute timespan; in considering patient preference information and with investigator consultation for subsequent infusions, subsequent infusions can be provided at either a 40-minute or 100-minute timespan. An IV ketamine drip will be initiated at a rate of 0.5 mg/kg for the 40-minute infusion or 0.3 mg/kg for the 100-minute infusion, for a total dose of 0.5 mg/kg. For example, an enrolled patient that weighs 75kg would receive a dose of 0.938mg/per minute in the 40-minute infusion, and in the 100-minute infusion, would receive a dose of .375 mg/per minute, for a total dose of 37.5mg in either 40-minute or 100-minute infusion. At Mayo Clinic (Rochester, MN), these infusions will be performed either in the

recovery room of the ECT suite for inpatients or at the Center for Clinical and Translational Science Clinical Research Unit (CRU) for outpatient infusions. CRU staff will be key to facilitating the execution of IV infusion procedures. CRU staff will collaborate to prepare infusion logistics, establish venipuncture site, monitor infusion and vital signs during and after infusion (60 minutes). These infusions will be given at least every other day (minimum of 1 day between infusions, and a maximum of 4 days between infusions). All infusions will be completed within a window of 5 to 11 days where the window includes the first infusion day ( $t_0$ ). The allowable time window is defined in quantitative terms as  $[t_0, t_0 + 11]$ . If the final infusion date is designated as  $t_x$ , then a given date for  $t_x$  is allowable if  $t_x < t_0 + 11$ .

For example, if the first infusion day was January 11, 2016 (a Monday), the participant could complete their second infusion on January 13, 2016 (Wednesday) and their final infusion on January 15, 2016 (a Friday). Friday's infusion date corresponds to a  $t_x$  value of 5, and is allowable. The final 24 hour post-infusion assessment would take place on January 16, 2016 (Saturday).

Alternatively, a participant who receives infusion 1 on a Tuesday could receive infusions 2 and 3 on Thursday during the same calendar week and Monday the following calendar week. In this case,  $t_x$  takes a value of 7, which is within the allowable 11-day time window including the first infusion.

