## A. BRIEF SUMMARY

This multi-site (Johns Hopkins Hospital, Mayo Clinic (Rochester, MN), Pine Rest Christian Mental Health Services, University of Michigan, and the University of Pennsylvania), open-label, single-arm clinical trial is designed to develop preliminary biomarkers of ketamine response in 100 patients with treatment-resistant non-psychotic unipolar major depression (MDD) or bipolar I or II depression (BPD). Ketamine will be administered intravenously (IV) at a subanesthetic dose of 0.5 mg/kg delivered over 40-minutes or 100-minutes of infusion time. Enrolled subjects will receive a total of three acute phase infusions, delivered at least every other day, within a time window of up to 11 days including the first infusion day. The primary outcome will be remission, as defined by a Montgomery-Åsberg Depression Scale (MÅDRS) score  $\leq 9$ . The secondary outcome measures include reduction of suicidality, as defined by a 50% reduction in the Beck Scale for Suicidal Ideation (BSS). Exploratory biomarkers for ketamine treatment outcome include baseline to endpoint change in WBC stimulated mTOR, AKT, and GSK3 signaling. Additional sample for the ascertainment of other biomarkers will also be taken.

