### Administration of study drug.

In the acute phase, the first infusion will be provided at a 40-minute timespan; in considering patient preference information and with investigator consultation for subsequent infusions, subsequent infusions can be provided at a 40-minute timespan. An IV ketamine drip will be initiated at a rate of 0.5 mg/kg for the 40-minute infusion or 0.3 mg/kg for the 100-minute infusion, for a total dose of 0.5 mg/kg. For example, an enrolled patient that weighs 75kg would receive a dose of 0.938mg/per minute in the 40-minute infusion, and in the 100-minute infusion, would receive a dose of .375mg/per minute, for a total ketamine dose of 37.5mg in either 40-minute or 100-minute infusion. Any patient preference information for infusion will be considered in consultation with investigator; for example, a patient that describes any side effect as unendurable subject to the 40-minute infusion, may express that they would instead prefer subsequent 100-minute infusions. Any subject enrolled that weighs ≥100kg will be dosed at 50mg maximum of ketamine. This dosage and rate of ketamine infusion are low enough that the presence of an anesthesiologist should not be required, although each site may have the option for an anesthesiologist to be present if desired. Instead, ketamine infusions at this low dose and rate can be administered by nursing staff. A study psychiatrist will be on site during all infusions, and will thus be immediately available as required for clinical ratings and for problems that may arise during the course of infusion. After the 40-minute or 100-minute infusion is completed, the participant's IV access will be discontinued and the participant will be monitored for an additional 60 minutes by study staff and/or other qualified site-specific designees (see §E.5.a). The study psychiatrist will be on site during this 60 minute period following ketamine infusion, as well.

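### The two ketamine drip rates carry no time unit, and no common unit makes both give the stated total of 0.5 mg/kg

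*Combined protocol and SAP*

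**What the plan says.** Section E.6 (Acute-Phase Administration of Ketamine) sets the drip at a "rate of 0.5 mg/kg for the 40-minute infusion or 0.3 mg/kg for the 100-minute infusion, for a total dose of 0.5 mg/kg". The same clause is repeated in E.6.b under Administration of study drug. No time unit is attached to either rate in either place.

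Both sections then give an example for a 75 kg patient, this time with units. In E.6 the patient "would receive a dose of 0.938mg/per minute in the 40-minute infusion" and 0.375 mg per minute in the 100-minute infusion, "for a total dose of 37.5mg in either 40-minute or 100-minute infusion". In E.6.b the 100-minute part of the example reads "would receive a dose of .375mg/per minute, for a total ketamine dose of 37.5mg in either 40-minute or 100-minute infusion".

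Elsewhere the dose is given as a total only. The Brief Summary describes a "subanesthetic dose of 0.5 mg/kg delivered over 40-minutes or 100-minutes of infusion time", and E.1 likewise gives 0.5 mg/kg for both durations.

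E.8.c applies the acute-phase administration procedures to the optional continuation phase of up to four further infusions.

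**The concern.** A rate needs a time unit, and the parallel wording of the two figures leads a reader to expect the same unit for both. No such unit exists. The slower infusion lasts 2.5 times as long, so its rate must be 2.5 times lower to give the same total, and the printed figures are not in that proportion. The sentence that sets the weight-based rate therefore disagrees with the total stated at its own end.

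This is the instruction staff would use to run an intravenous infusion. It governs three acute infusions for every subject, and E.8.c carries it into the continuation phase. E.6.b says that "ketamine infusions at this low dose and rate can be administered by nursing staff". E.14 counts a subject's receiving a wrong dose among major protocol violations, so the text against which dosing is judged should not contradict itself. The number of patients, the design and the analysis do not depend on this sentence.

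**Working it through.** **Inputs** (all from E.6, repeated in E.6.b): rates 0.5 mg/kg (40 minutes) and 0.3 mg/kg (100 minutes), no time unit; stated total 0.5 mg/kg for either duration; example weight 75 kg with 0.938 and 0.375 mg per minute and a total of 37.5 mg.

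**1. Reproduce the plan's example.** Total = rate per minute × minutes.

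- Stated total at 75 kg: 0.5 × 75 = 37.5 mg.
- 40-minute infusion: 0.938 × 40 = 37.52 mg (the unrounded rate is 37.5/40 = 0.9375).
- 100-minute infusion: 0.375 × 100 = 37.5 mg.

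The example and the stated total agree, apart from rounding.

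**2. Test that needs no unit.** Equal totals over 40 and 100 minutes require a rate ratio of 100/40 = 2.5. The example gives 0.938/0.375 = 2.50. The printed weight-based rates give 0.5/0.3 = 1.67.

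**3. Solve for the unit.** Let the rates be per U minutes. Total in mg/kg = rate × minutes / U.

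- 40-minute infusion: 0.5 × 40/U = 20/U, which equals 0.5 only if U = 40.
- 100-minute infusion: 0.3 × 100/U = 30/U, which equals 0.5 only if U = 60.
- Ratio of the two totals: 30/20 = 1.5 for every U, against 1.0 as stated.

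**4. Size at 75 kg.** The totals are 75 × 20/U = 1500/U mg and 75 × 30/U = 2250/U mg, against 37.5 mg.

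| Reading of both rates | 40-minute infusion | 100-minute infusion |
|---|---|---|
| per 40 minutes | 37.5 mg (agrees) | 56.25 mg (+50%) |
| per hour | 25 mg (−33%) | 37.5 mg (agrees) |
| per 100 minutes | 15 mg (−60%) | 22.5 mg (−40%) |
| amount per infusion (not a rate) | 37.5 mg (agrees) | 22.5 mg (−40%) |

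Every row conflicts with the stated total for at least one duration. The rows show what follows from each reading; they are not a range of expected doses.

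**5. Compare on one scale.** Converted to mg/kg per hour, the example's rates are 0.5/40 × 60 = 0.75 and 0.5/100 × 60 = 0.30. The second matches the printed 0.3 if that is read per hour. The first does not match the printed 0.5 read the same way.

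**The case against.** The strongest reply is that the text supplies its own remedy. The total stands in the same sentence, and the next sentence gives rates with units for both durations. That consistent material is also printed twice. It agrees with the Brief Summary and E.1. The 50 mg maximum in E.6.b for subjects of 100 kg or more agrees too, since 0.5 × 100 = 50. A reading that gives 56.25 mg at 75 kg would exceed that maximum, so it is unlikely to be taken as intended. A rate without a unit cannot be set on a pump anyway, so staff must go to the total or the example. There are further safeguards: "A study psychiatrist will be on site during all infusions", and under E.5.e "the research pharmacy will be contacted to prepare the ketamine infusion".

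It can also be said that the plan never claims a common unit. Read per 40 minutes for one figure and per hour for the other, both rates give 0.5 mg/kg, so the defect could be called missing or mixed units.

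Most of this stands as a limit on severity. It makes an actual dosing error less likely, and the alternative doses above should carry little weight by themselves. It does not repair the sentence. Neither unit is printed, and a reader can find the mixed pair only by working back from the total. The example covers a single weight, and the sentence meant to state the rate for any weight is the one that fails. Loss of a unit when the PDF was read is not a good explanation: the clause is the same in two places, the per-minute units beside it survived, and restoring any one unit would leave the 1.5-fold conflict.

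**Conclusion.** The concern holds. The two drip rates have no time unit, and no common unit lets both deliver the stated 0.5 mg/kg; the implied totals always differ by a factor of 1.5. The stated total, the per-minute example and the weight cap are mutually consistent, so the conflict lies between the rate figures and the rest of the text.

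The factor of 1.5 rests only on the printed figures and on both rates sharing one unit. The milligram amounts also rest on the 75 kg example and on the rates being used without the total and example beside them. No misdosing is shown, and nothing statistical changes. The point should be fixed because it sits in an operative administration instruction, not because of the hypothetical doses.

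**What to change.** The sponsor should reconcile the rate sentence, the stated total and the worked example in E.6 and in Administration of study drug (E.6.b), and give every rate an explicit time unit on one common scale. A simple check on the revised text is that rate × duration returns the stated total for both infusion lengths. Which figures stand is the sponsor's decision; none is proposed here.

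The change is wording only. Under E.2 it still needs an amendment issued by the sponsor, signed and dated by the investigator and approved by each site's IRB/IEC, so it could be combined with other corrections. Design, sample size and analysis stay as they are.
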